- l. Subjects who have standard of care CT/MRI results may use these results in lieu of the Screening CT/MRI required for this study, provided the CT/MRI was done within 28 days of first dose and was acquired in accordance with the guidelines outlined in Section 8.1.1.
- m. Bone marrow aspiration and biopsy will be done at screening or within 60 days before the first dose of study drug per clinical guidelines. Bone marrow biopsy and aspirate, MRD assessment can be tested on Cycle 1 Day 1 pre-dose if not performed during screening.
- n. If the subject's physical examination findings, laboratory evaluations, and radiographic evaluations suggest that CR has been achieved, a confirmatory bone marrow aspirate/biopsy must be obtained to confirm the CR.
- o. If the subject's physical examination findings, laboratory evaluations, and radiographic evaluations suggest that PR, CR, or CRi has been achieved, a peripheral blood (PB) and bone marrow (BM) sample to evaluate MRD status (flow based) should be done between 8-12 weeks from the time of supportive clinical assessments, including CT imaging of suspected PR, CR, or CRi. If MRD samples are not taken at EoT visit, the samples can be drawn at SFU visit. After final analysis(FA) and per Amendment 5.0, MRD tests are not mandatory and will be locally performed per clinical practice.
- p. CCI
- q. After Cycle 7 Day 1, CCI serum immunoglobulins, β 2-microglobulin, and T/B/NK counts should be collected every 24 weeks, beginning with Cycle 13. After FA and per Amendment 5.0, CCI are not required, laboratory assessments including serum immunoglobulins, β 2-microglobulin, and T/B/NK are not required and will be locally performed if necessary per the discretion of investigator.
- r. Hematology assessments also conducted as part of safety activities. After FA and per Amendment 5.0, hematology testing will be performed locally.
- s. Blood sample for Cytogenetics and genetic molecular prognostic molecules, FISH evaluation will also be drawn when a subject has a disease-progression, at the end of treatment visit or a safety follow-up visit. After FA and per Amendment 5.0, Cytogenetics and genetic molecular prognostic molecules and FISH are not required and will be locally performed per the discretion of investigator.

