4.1 Overall design

This randomized, regional, multicenter, open-label, Phase 3 study will evaluate the efficacy and safety of acalabrutinib monotherapy versus chlorambucil plus rituximab in subjects with previously untreated CLL without del(17p) or TP53 mutation.

Approximately 150 subjects will be randomized in a 1:1 ratio into 2 treatment arms (n=75 subjects each) to receive either acalabrutinib monotherapy (Arm A) or rituximab in combination with chlorambucil (Arm B). It is planned to randomize approximately 75 to 120 patients in total (50% to 80% of total sample size) from China. Randomization will be stratified by ECOG [0-1 versus 2] and Rai stage [0-II versus III-IV]. A schedule of screening and trial assessments is provided in [Table 1](#) (Arm A) and [Table 2](#) (Arm B).

At investigator discretion, subjects randomized to Arm B who have BICR-confirmed or investigator-assessed (after FA and per Amendment 5.0) disease progression and meet eligibility for crossover are permitted to receive acalabrutinib monotherapy treatment until disease progression or unacceptable toxicity. For the details, please refer to [Section 6.8](#).

Subject participation will include a screening phase, treatment phase, post-treatment disease follow-up phase, and survival follow-up phase. The screening phase will last up to 28 days before the first dose of study drug, during which the subject's eligibility and baseline characteristics will be determined. The treatment phase will last from randomization until study drug(s) discontinuation. Treatment with acalabrutinib may be continued until disease progression or any other treatment discontinuation criterion is met. Treatment with chlorambucil/rituximab is up to 6 cycles, or until there is disease progression or any other treatment discontinuation criterion is met. Dose modification provisions are provided in [Section 6.6](#).

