For gradable parameters, a summary of worst post-baseline toxicity grade will be provided in the “on-treatment” period by treatment arm. Appropriate summaries of laboratory data over time and change from baseline will be provided by treatment arm.

Analysis of Lymphocytosis

For all subjects with baseline and any post-baseline ALC measurements, ALC at peak summary will be provided by treatment arm.

Lymphocytosis is defined as an ALC >5000 cells/ μ L and an increase above baseline. The number of subjects with at least one occurrence of lymphocytosis will be summarized. For subjects with lymphocytosis, resolution of lymphocytosis is defined as 1) a decrease of ALC value to the baseline level or lower, or 2) an achievement of ALC value that is below 5,000 cells/ μ L, whichever occurs first. The following analyses will be conducted for subjects with lymphocytosis by treatment arm: ALC at peak and time to peak ALC for subjects who have lymphocytosis. The data will be summarized by descriptive statistics.

Duration of lymphocytosis is defined as the duration of time from the earliest date on which the ALC value met the lymphocytosis criteria at a post-baseline assessment to the earliest date on which a subsequent ALC value met the resolution criteria.

Analysis of Serum Immunoglobulins

Serum immunoglobulins (IgA, IgG, and IgM) are collected as scheduled in the SoA. For each variable, descriptive statistics will be presented at each scheduled post-baseline assessment by treatment arm. Subjects who received IVIG on the study will be excluded from the summary for IgG.

ECOG Performance Status

The ECOG performance status will be collected as scheduled in the SoA. The ECOG performance status grade ranges from 0–5. Descriptive statistics and change from baseline will be provided for each visit over time.

Weight

Descriptive statistics and change from baseline will be provided over time.

Vital signs

Vital sign parameters will be presented for each treatment group. Summary statistics for continuous variables cover n, mean, SD, Min, Q1, median, Q3, and Max. Frequency tables cover number and percentage of subjects in the respective category.

For each scheduled post-baseline visit, descriptive statistics for all vital sign parameters will be presented for observed values and change from baseline.

Details of vital signs analyses will be provided in the SAP.

9.5.3

CCI

[REDACTED]

[REDACTED]

[REDACTED]

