#### **4.2.6.3 Clinical laboratory data**

Laboratory data obtained until 30 days after the last dose of study treatment or the start of a subsequent therapy (including crossover treatment), whichever occurs first, will be used for reporting. Project-specific reference ranges will be applied for relevant laboratory variables (hematology, clinical chemistry).

Hematology, clinical chemistry, T/B/NK Cell Count and Serum Immunoglobulin will be listed individually by patient and suitably summarized and may be plotted as needed. Patients who received IVIG on the study will be excluded from the summary for IgG. For all laboratory variables, which are included in the version 5.0 of NCI CTCAE, the NCI CTCAE grade will be calculated.

Numerical laboratory data (absolute and change from baseline) will be summarized by scheduled visit using standard summary statistics (mean, standard deviation, minimum, median, maximum, and number of observations).

For hematology and clinical chemistry, where applicable, data shift tables will summarize the change from baseline to maximum on-treatment NCI CTCAE grade, the change from baseline to maximum value, and the change from baseline to minimum value.

Central laboratory data will be used for summaries of hematology, however local laboratory data will be used when central data is not available. All laboratory hematology data will be summarized together, regardless of whether the tests were performed for safety purposes or for evaluation of disease response. Summary of T/B/NK cell count will be based on central laboratory data. Summaries of clinical chemistry and serum immunoglobulin levels will use local laboratory data.

To identify potential Hy's Law (see CSP Appendix D for further details) cases, patients who meet any of the following criteria at any point during the study will be highlighted:

- $AST \geq 3 \times ULN$
- $ALT \geq 3 \times ULN$
- $TBL \geq 2 \times ULN$

For all patients who meet the biochemical criteria for Hy's Law (potential Hy's Law), the relevant laboratory parameters will be tabulated showing all visits for these patients.

Any data outside the laboratory reference ranges will be flagged and explicitly noted on the listings that are produced. To help identify potential Hy's Law cases, patients who have  $ALT$  or  $AST \geq 3 \times ULN$  or total bilirubin  $\geq 2 \times ULN$  at any time during the study (i.e. not necessarily at the same time) will be flagged in the listings.

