All laboratory results will be listed.

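### The IgG summary drops the whole patient after any on-study IVIG, so valid pre-infusion values are lost; a minor point, and the direction of the shift rests on an assumption

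*SAP*

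**What the plan says.** The rule appears twice in almost identical words. Protocol 9.5.2, under the serum immunoglobulin analysis, states: "Subjects who received IVIG on the study will be excluded from the summary for IgG". SAP 4.2.6.3 states: "Patients who received IVIG on the study will be excluded from the summary for IgG". Neither limits the exclusion to values taken after an infusion, and neither defines *on the study*.

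The SAP fixes what the exclusion acts on: "Numerical laboratory data (absolute and change from baseline) will be summarized by scheduled visit using standard summary statistics". The protocol describes the immunoglobulin output more narrowly: "For each variable, descriptive statistics will be presented at each scheduled post-baseline assessment by treatment arm". IgA and IgM have no such exclusion.

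The reporting window is "Laboratory data obtained until 30 days after the last dose of study treatment or the start of a subsequent therapy". The schedules of assessments (Protocol 1.1, Tables 1 and 2) place immunoglobulins at Cycle 1 Day 1 and Cycle 7. The footnote on later sampling says that immunoglobulins, β2-microglobulin and "T/B/NK counts should be collected every 24 weeks, beginning with Cycle 13".

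Excluded patients do not vanish from the report, since "All laboratory results will be listed". No count of patients excluded for IVIG is planned, nor an IgG summary that includes them. The documents do not say why IVIG would be given, how often, or what IgG levels are expected.

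**The concern.** An infusion can alter only IgG measured after it. A rule that removes the whole patient also discards values drawn beforehand, so who appears in the baseline and Cycle 7 rows depends on what happens to them later. That is selection on a future event, and it can favour one end of the IgG distribution if IVIG use is related to IgG.

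The opportunity for exclusion differs by arm. Acalabrutinib continues to progression, whereas "Treatment with chlorambucil/rituximab is up to 6 cycles". An Arm A patient can lose the Cycle 7 value because of IVIG given much later; the corresponding exposure in Arm B may be far shorter. At stake is whether a reader can take the by-arm IgG rows, particularly the early ones, as describing the randomised and treated patients.

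**Working it through.** The plan states no IgG level, IVIG rate or number excluded, so there is no figure to reproduce. The check covers timing, direction and possible size.

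**1. Which visits allow a comparison of arms.** With 28-day cycles kept to schedule:
- Last Arm B dose, Cycle 6 Day 15: 5 × 28 + 15 = day 155.
- Window closes: 155 + 30 = day 185.
- Cycle 7 Day 1: 6 × 28 + 1 = day 169, inside.
- Cycle 13 Day 1: 12 × 28 + 1 = day 337, outside.

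Cycle 7 Day 1 is therefore the main post-baseline visit with IgG in both arms.

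**2. How long each arm is exposed to the exclusion.** Protocol 6.5 records concomitant treatment to 30 days after last dose; on that reading Arm B is exposed to about day 185. SAP 4.2.8 says 30 days after discontinuation or objective progression, whichever is later; on that reading Arm B patients can be removed for IVIG given after their laboratory window has closed. Arm A is exposed to progression or beyond on either reading, unless treatment stops earlier.

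**3. Size at a single visit.** With f the fraction excluded and d the amount by which excluded patients' mean IgG lies below the arm mean:

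mean(kept) − mean(all) = f/(1 − f) × d

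Both f and d are assumed; 75 per arm is from Protocol 9.2.

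| f | Excluded of 75 | d = 0 | d = 2 g/L | d = 4 g/L |
|---|---|---|---|---|
| 5% | 3.8 | 0 | 0.11 | 0.21 |
| 10% | 7.5 | 0 | 0.22 | 0.44 |
| 20% | 15 | 0 | 0.50 | 1.00 |

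If 20% were excluded in one arm and 5% in the other, with no true difference, the arms would differ by 0.50 − 0.11 = 0.39 g/L (d = 2) to 1.00 − 0.21 = 0.79 g/L (d = 4).

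**4. Behaviour over time.** A simulation of 200,000 patients over five visits used these assumptions: baseline IgG lognormal with mean 7.5 and SD 3 g/L, drift −0.2 g/L per interval, and an IVIG boost of 2, 4 or 6 g/L. Mean of kept patients minus mean of all patients' own (endogenous) IgG, in g/L:

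| IVIG start | Excluded | Baseline | Last visit |
|---|---|---|---|
| Strongly driven by IgG < 4 g/L | 17% | +0.51 | +0.64 |
| Moderately driven | 13% | +0.22 | +0.26 |
| Unrelated to IgG | 15% | about 0 | about 0 |
| More frequent at IgG ≥ 4 g/L | 17% | −0.06 | −0.07 |

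The effect on change from baseline was at most +0.13 g/L.

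Against IgG as measured, IVIG effect included, the last-visit figure under strong selection was +0.29, −0.05 or −0.40 g/L for boosts of 2, 4 and 6. The rule then also removes values that IVIG had raised.

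**5. Dropping only values from the first IVIG onward.** Under strong selection (boost 6), the shift against endogenous IgG by visit is:

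| Rule | Baseline | 2nd | 3rd | 4th | 5th |
|---|---|---|---|---|---|
| Exclude patient | +0.51 | +0.57 | +0.62 | +0.64 | +0.64 |
| Exclude values from first IVIG | 0.00 | +0.12 | +0.28 | +0.45 | +0.64 |

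The baseline shift is zero in every scenario. At the last visit both rules keep the same patients, so nothing is gained there.

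**The case against.** The rule has a sound purpose, keeping infused immunoglobulin out of the IgG summary, and both documents prespecify it. It keeps one IVIG-free cohort across visits. Cutting at first IVIG produces a cohort that changes by visit, so mean IgG could appear to rise as low-IgG patients leave. Per-visit numbers of observations are shown, all results are listed with out-of-range values flagged, and concomitant medications are summarised by ATC class (SAP 4.2.8). Infection is assessed directly, through adverse events and the infection category of events of clinical interest (SAP 3.5.2). The protocol promises immunoglobulin statistics only at post-baseline visits, and IgG is not among the baseline characteristics in SAP 4.2.7.

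Most of this stands as an argument about severity. It does not justify deleting valid values: listings and counts do not correct the table, and the SAP's change from baseline uses the baseline value even if no baseline row is printed. The changing-cohort cost is real and must be stated.

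A reader might infer three stronger things.
- *That the IgG results are biased upward throughout.* This is not established. The documents never link IVIG to low IgG; the nearest hint is the word prophylactic in the hepatitis footnotes. Autoimmune cytopenia is a route to eligibility (Protocol 5.1), and the documents do not say how it is treated.
- *That the rule conceals harm on a key marker of humoral immunity.* The unredacted objectives (Protocol Table 4) name no immunoglobulin endpoint, and Protocol 8.6 and 8.8 say that pharmacodynamics and biomarkers are not evaluated.
- *That a false difference between arms exists.* The design makes it possible, but the documents give no IVIG use by arm.

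**Conclusion.** The point holds in a limited form. The wording removes pre-infusion IgG, including baseline and Cycle 7 Day 1, because of a later post-randomisation event, and the arms are exposed to that removal for different lengths of time. That follows from the documents alone.

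Direction and size do not. An upward shift in patients' own IgG at baseline and early visits requires that IVIG goes mainly to patients with low IgG. Under the assumed ranges it runs from zero to about 1 g/L at a given visit, and it is slightly negative if IVIG is more frequent at higher IgG. At late visits the sign against measured IgG is indeterminate.

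Severity is minor: the summary is descriptive, and no hypothesis test or primary conclusion depends on it.

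**What to change.** Apply this rule to the IgG summary: *IgG values on or after the first on-study IVIG dose are excluded; baseline and all pre-IVIG values are retained. The number of patients excluded for IVIG is shown by arm and visit beside the table, and patients who received IVIG before entry are flagged.* State the dates between which IVIG counts as on study, since Protocol 6.5 and SAP 4.2.8 give different ends to the recording period.

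The Protocol 1.2 synopsis reports that the 3 January 2024 data cut-off was treated as the final analysis and the study was unblinded. The practical form is therefore a supplementary table in the study report, labelled as added afterwards, beside the prespecified one. It should carry a note that selective loss of IVIG users at late visits remains.

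The cost is one programming condition and a few table rows, with no new data. Protocol 6.5 requires start and end dates for concomitant medication, and SAP 4.2.4 already has rules for incomplete start dates. One limit: Protocol 6.5 looks back only 4 weeks before treatment, while the hepatitis footnotes contemplate IVIG within 3 months before enrolment, so the pre-entry flag may be incomplete.

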### **Analysis of Lymphocytosis**

For all patients with baseline and any post-baseline ALC measurements, ALC at peak summary will be provided.

The number of patients with at least one occurrence of lymphocytosis will be summarized. The following analyses will be conducted for patients with lymphocytosis by treatment arm: ALC at peak, time to lymphocytosis and duration of lymphocytosis for patients who have lymphocytosis will be summarized with descriptive statistics.

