In particular, given the known mechanism of action of BCR-inhibiting agents including acalabrutinib, treatment-related lymphocytosis is an expected and frequent phenomenon observed with initiation (or re-initiation) of BTK inhibitors. An increase in blood lymphocyte count by itself does not uniformly indicate an increased tumor burden but may reflect redistribution of leukemia cells from lymphoid tissues to the blood. In such cases, increased lymphocytosis alone is not a sign of treatment failure or PD. The investigator may use their clinical judgment when assigning the overall response with blood lymphocyte count, as necessary.

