## **Lymphocytosis**

Lymphocytosis is defined as an ALC > 5000 cells/ $\mu$ L and an increase 50% or more from baseline.

Duration of lymphocytosis is defined as the duration of time from the earliest date on which the ALC value met the lymphocytosis criteria at a post-baseline assessment to the earliest date on which a subsequent ALC value met the resolution criteria.

For patients with lymphocytosis, resolution of lymphocytosis is defined as 1) a decrease of ALC value to the baseline level or lower, or 2) an achievement of ALC value that is below 5,000/ $\mu$ L, whichever occurs first.

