## **4. ANALYSIS METHODS**

### **4.1 General Principles**

The primary objective of the study is to test the following hypothesis:

H0: BICR-assessed PFS of Arm A is the same as Arm B

H1: BICR-assessed PFS of Arm A is not the same as Arm B

The study will be considered positive (a success) if the primary PFS analysis result for Arm A versus Arm B is statistically significant.

The below mentioned general principles will be followed throughout the study:

- Descriptive statistics will be used for all variables, as appropriate. Continuous variables will be summarized by the number of observations, mean, standard deviation, median, upper and lower quartiles minimum, and maximum. For log-transformed data it is more appropriate to present geometric mean, coefficient of variation (CV), median, minimum and maximum. Categorical variables will be summarized by frequency counts (n) and percentages (%) for each category.
- Unless otherwise stated, percentages will be calculated out of the total number of patients in the analysis set for the corresponding treatment group. Overall totals (i.e. data from Arm A and Arm B combined) will be calculated for baseline summaries only.
- For continuous data, the mean and median will be rounded to 1 additional decimal place compared to the original data. The standard deviation will be rounded to 2 additional

decimal places compared to the original data. Minimum and maximum will be displayed with the same accuracy as the original data.

- For categorical data, percentages will be rounded to 1 decimal place.
- SAS® version 9.4 will be used for all analyses.

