Missing safety data will generally not be imputed. However, safety assessment values of the form of “< x” (i.e. below the lower limit of quantification) or > x (i.e. above the upper limit of quantification) will be imputed as “x” in the calculation of summary statistics but displayed as “< x” or “> x” in the listings. Additionally, adverse events that have missing causality (after data querying) will be assumed to be related to study drug.

Furthermore:

- For missing diagnostic dates, if day and/or month are missing use 01 and/or Jan. If year is missing, put the complete date to missing.
- For missing AE and medication/radiotherapy start dates, the following will be applied
  - a. Missing day- Impute the 1st of the month unless month is the same as month of the first dose of study drug then impute first dose date
  - b. Missing day and month -Impute 1st January unless year is the same as first dose date then impute first dose date

- c. Completely missing-impute first dose date unless the end date suggests it could have started prior to this in which case impute the 1st January of the same year as the end date
- For missing AE and medication/radiotherapy end dates, the following will be applied:
  - a. Missing day - Impute the last day of the month
  - b. Missing day and month – impute 31st December. Flags will be retained in the database indicating where any programmatic imputation has been applied, and in such cases, any durations would not be calculated.

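### Duration of lymphocytosis has no rule for unresolved patients, so the planned descriptive summary would run short and is not comparable between arms

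*SAP*

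**What the plan says.** SAP 3.5.3 (Lymphocytosis) fixes the start: "Duration of lymphocytosis is defined as the duration of time from the earliest date on which the ALC value met the lymphocytosis criteria" after baseline. The only end point is a later count: the clock runs "to the earliest date on which a subsequent ALC value met the resolution criteria". Resolution means a return to baseline or below, or an ALC under 5,000/µL, whichever is first. Protocol 9.5.2 defines duration the same way.

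SAP 4.2.6.3 (Analysis of Lymphocytosis) reports by arm and says that "duration of lymphocytosis for patients who have lymphocytosis will be summarized with descriptive statistics". SAP 4.1 explains what that means for continuous data: "Continuous variables will be summarized by the number of observations, mean, standard deviation, median, upper and lower quartiles minimum, and maximum". SAP 4.2.4 adds: "Missing safety data will generally not be imputed".

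SAP 4.2.6.3 also limits reported laboratory data to the period ending 30 days after last dose or at the start of subsequent therapy or crossover, whichever is earlier. SAP 4.2.3 excludes data after the cut-off, apart from the survival sweep. Kaplan-Meier methods appear in SAP 4.2.2.1, for the time-to-event efficacy endpoints only.

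**The concern.** Duration of lymphocytosis is a time-to-event quantity handled as a complete measurement. A patient whose ALC has not met the resolution criteria when observation stops has an onset date and no end date. Under the definition no duration can be derived, and the SAP supplies no substitute. Long episodes are the ones most likely to be cut off, so the loss is selective and shortens the summary.

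Protocol 8.1.1 says that "treatment-related lymphocytosis is an expected and frequent phenomenon observed with initiation (or re-initiation) of BTK inhibitors". How long it lasts is what a reader would take from this table. A figure based only on patients who resolved answers a different question without saying so. The by-arm layout adds a second problem, because the two arms are observed for very different lengths of time.

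**Working it through.** **1. What happens to an unresolved patient.** Start date: defined. End date: only a later ALC meeting resolution. Censoring date: none given. Imputation: generally none for safety data. The duration is therefore missing and leaves the n, mean, median and quartiles. By contrast, duration of response, which also runs from an onset to an end event, is given event and censoring rules (SAP 3.3.4) and Kaplan-Meier analysis (SAP 4.2.2.5).

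**2. Observation windows by arm.** Arm B has at most 6 cycles of 28 days (SAP 1.2). The last planned chlorambucil dose is Cycle 6 Day 15, which is day 5 × 28 + 15 = 155. Adding 30 days closes the window at about day 185 if there are no dose delays. Arm A is treated until progression or another reason to stop. With accrual of about 30 months (SAP 1.3) and final analysis at about 45 months (Protocol 4.4), Arm A's potential follow-up is 45 − 30 = 15 months up to 45 months.

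**3. Direction in closed form.** The documents state no lymphocytosis duration, so there is no figure to reproduce. Assume exponential resolution (rate λ) and independent exponential censoring (rate μ). Resolved durations then have median ln 2/(λ + μ), and the fraction resolved is λ/(λ + μ). Hence the resolved-only median equals the true median × the fraction resolved. With 10%, 20%, 30% or 50% unresolved, it is 90%, 80%, 70% or 50% of the truth.

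**4. Arm A on the protocol visit grid (simulation, 20,000 patients per row).** Assumptions that are not in the documents: onset on day 8, exponential duration, and 10% a year stopping treatment. Resolution is dated at the first scheduled hematology visit that shows it.

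| Assumed true median (months) | Unresolved | Resolved-only median | Kaplan-Meier median | Resolved-only vs truth |
|---|---|---|---|---|
| 3 | 4% | 3.4 | 3.4 | about equal |
| 6 | 12% | 5.3 | 8.0 | 1 − 5.3/6 = 12% low |
| 12 | 29% | 8.0 | 13.6 | 1 − 8.0/12 = 33% low |
| 18 | 42% | 10.8 | 19.1 | 1 − 10.8/18 = 40% low |

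Both estimators move in visit steps. Cycle 7 Day 1 is day 169 and Cycle 10 Day 1 is day 253. From day 8 these give 161 days (5.3 months) and 245 days (8.0 months). I reran the same set-up with other stop rates. At 20% a year the resolved-only medians do not change. At zero, the 6-month row moves up one step to 8.0 and its shortfall disappears, and the 12-month row becomes 10.8.

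**5. Arm B, window closed at day 185.** At assumed true medians of 3, 6, 12 and 24 months, 29%, 54%, 74% and 86% are unresolved. The resolved-only medians are 2.5, 2.5, 2.5 and 3.4 months. Kaplan-Meier gives 3.4 months at 3 and is not reached at 6, 12 and 24. The planned figure would mostly reflect the window.

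**6. The other reading: keep unresolved patients, cut at last ALC.** In Arm A the median is 10.8 months at a true 12 and 16.3 at a true 24. In Arm B it is 5.3 at true medians of 6, 12 and 24. Long durations are still understated.

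**The case against.** Several points against this are sound.

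- **Exclusion is inferred.** The SAP says duration is summarised for patients who have lymphocytosis; it does not say that unresolved patients are left out. A reader might take exclusion as a stated rule. It follows only from the definition and the no-imputation convention. The alternative reading in step 6 does not remove the bias, and leaving the choice to the programmer is itself a gap.
- **The omission would be visible.** The number with lymphocytosis and the n behind the duration summary are both planned, so a shortfall would show. All laboratory results are also listed. This lets an attentive reader see the problem but does not correct the median.
- **A larger bias is tempting to quote.** Setting the resolved-only median against Kaplan-Meier gives about 34% to 43% at true medians of 6, 12 and 18 months (5.3 vs 8.0, 8.0 vs 13.6, 10.8 vs 19.1). Kaplan-Meier does estimate the visit-dated duration that the SAP defines. But visit spacing puts it above the assumed truth, and the 6-month contrast is exactly one visit step. That range should not be read as error against the true duration.
- **The size rests on assumptions.** Neither document gives a resolution time, the share of patients with lymphocytosis or the share unresolved. If nearly all cases resolve early, there is nothing to correct.
- **The consequence is limited.** A reader might infer that a short reported duration would distort progression calls. The documents do not support this. Protocol 8.1.1 says lymphocytosis alone is not progression and leaves the matter to clinical judgment. No duration cut-off is used anywhere, and SAP 3.2 says responses are not derived programmatically.
- **The protocol asks for little here.** Section 9.5.2 defines duration but lists only peak ALC and time to peak for descriptive summary, and the synopsis says safety data are not formally analysed. A Kaplan-Meier median is still a description, not a test.

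**Conclusion.** The concern holds as a gap in a supportive safety summary. Duration of lymphocytosis has no rule for patients whose ALC has not resolved when observation ends, and either simple way of programming it shortens long durations. The by-arm figures cannot be compared, because Arm B's window closes near day 185 and Arm A's stays open while treatment continues.

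The actual size is unknown. In Arm A, with exponential resolution and 10% a year stopping treatment, the resolved-only median is about equal to the truth at 3 months and about 12%, 33% and 40% low at 6, 12 and 18 months. The 12% depends on the visit grid and the stop rate. The primary PFS test, its alpha, the sample size and response assignment are unaffected.

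**What to change.** In SAP 4.2.6.3, estimate duration of lymphocytosis by Kaplan-Meier. Censor unresolved patients at their last ALC on or before the earliest of data cut-off, the end of the laboratory reporting window, and the start of subsequent therapy or crossover. Report the median with 95% CI and the number (%) resolved and unresolved by arm. Add a note that resolution is dated at the visit where it is seen, so medians run long by up to one visit interval (12 weeks from Cycle 7 on). Keep the descriptive summaries of peak ALC and time to lymphocytosis.

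The cost is one SAP sentence and one extra supportive table on ALC data already collected. The median may be not reached in Arm B, which is itself the correct message when the window is short. Because Protocol 1.2 records that the final analysis has taken place, the table can be added as a supplement.
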